3.1.2 COLLECTION AND PROCESSING OF BIOLOGICAL SAMPLES

We will collect blood, urine, and tumor specimens. The collected blood will be used for the analysis of genotypes and the measurement of hormone, cytokine, and eicosanoid concentrations in serum and plasma. Urine samples are collected to study the association between inflammation of the prostate and the progression of the disease. The collected urine will be analyzed for markers of inflammation and oxidative stress such 8hydroxydeoxyguanosine, malondialdehyde, nitrate/nitrite, and metabolites of the eicosanoid pathway. We are also planning to measure nicotine metabolites in urinary samples to study the association between nicotine metabolism, genetic polymorphisms, and the risk of advanced prostate cancer. The tissue specimens are collected for wholegenome gene expression analysis and the preparation of tissue arrays for immunohistochemical analysis of protein expression.

The collection of blood, urine, and tissue specimens, will follow procedures that have been established for our protocol titled "Resource for the collection and evaluation of human tissues and cells from donors with an epidemiology profile", University of Maryland at Baltimore IRB #0298229. The same procedures are used in the lung cancer case-control study. For surgical specimens, each late afternoon one of the lab personnel checks the schedule for possible tissues. A note that reminds the operating room (OR) personnel to send the resected specimen to the pathology fresh, not fixed, is given to the OR. When the resection of a tumor is done, the OR will call the University of Maryland Department of Pathology. A designated person will transport the tissue to the pathology, where the tissue is procured as soon as possible. All biological samples will be stored at the pathology until further notice. The procedures are as follows.

PROCEDURES FOR COLLECTION OF BLOOD AND URINE

- 1. Observe universal precautions for prevention of transmission of blood-borne pathogens
- 2. Clean skin with alcohol wipe and wait to dry
- 3. Obtain blood: one 15 cc red top tube, two or three 10 cc green top tubes and one 10 cc red-green top tube. Apply pressure and band-aid
- 4. Place blood samples on ice
- 5. Request urine sample in plain sterile container (50 ml)

PROCEDURES FOR PROCESSING OF BLOOD AND URINE AT THE UNIVERSITY OF MARYLAND DEPARTMENT OF PATHOLOGY

- 1. Storage of urine at -70° C in 10 ml aliquots
- 2. Cryopreserve four 2 ml of whole heparinized blood
- 3. Send seven cc of heparinized whole blood to LHC within 24 hours for lymphocyte cultures by messenger
- 4. Separation of buffy coat from red cells and plasma. Wash red blood cells according to protocol. Storage of all three at -70° C
- 5. Separation of lymphocytes from red blood cells and plasma. Wash red blood cells according to protocol. Cryopreservation of two 0.5 ml tubes of lymphocytes. Storage of all tubes at -70° C

PROCEDURES FOR TISSUE COLLECTION

- 1. Tissues are collected at time of prostatectomy
- 2. Notify surgeon and the pathology department of tissue collection
- 3. A designated person will take tumor specimen as fast as possible, but within 10min of resection, to the pathology room
- 4. A pathology technician will immediately process the sample.
- 5. Within 20min of receipt, place half of the specimen in a pre-labeled container. Immediately flash-freeze and store the container at -70° C
- 6. Within 20min of receipt, place about a quarter to a third of the specimen in a prelabeled container and cover with OCT. Immediately flash-freeze the OCTembedded tissue and store the container at -70° C. The specimen will be processed at a later time point for laser-captured microdissection. If a specimen does not contain tumor, a flash-frozen tissue piece from step 5 can be used to replace the sample
- 7. Prepare a paraffin block of remaining tissue section
- 8. Prepare a H/E slide for diagnosis by pathologist

3.1.3 ASSESSMENT OF DISEASE STAGE AND OUTCOME

Information on disease stage, metastasis and outcome (relapse and survival) will be obtained from pathology and medical records, Veteran Administration databases, State of Maryland records, and from the National Death Index.

3.1.4 RESEARCH LABORATORY STUDIES

Genotyping at the NCI

- Isolate DNA from whole blood or buffy coat using a previously tested DNA isolation kit
- Determine DNA quality
- Perform genotype analysis with quality-controlled assays. Each assay will contain negative and positive controls, and 10% blinded duplicates

Gene expression analysis at the NCI

- Cut fresh-frozen tissue into serial 8µ section
- Microdissect tissue into tumor and non-tumor tissue, using laser-captured microdissection (LCM). A pathologist will help with the procedure. The equipment for LCM is provided by the NCI core facility
- Isolate, amplify and label RNA, using existing protocols. Currently, our laboratory uses a QIAGEN protocol for the isolation of total RNA from microdissected tissue and the small sample labeling protocol by Affymetrix to produce biotin-labeled cRNA
- Hybridize cRNA onto the Affymetrix GeneChip arrays
- Data analysis will be performed in collaboration with a biostatistician. We have established such collaboration for gene expression analysis of breast cancer

3.1.5 LIMITATIONS OF THE CASE-CONTROL DESIGN

A frequent limitation of case-control studies is the heterogeneity of the population as it relates to race, age, and catchment area. If not addressed, the study may yield differences in genetic frequencies that are unrelated to the case status. To correct for the problem, we have restricted the study to a narrow geographic area, and will match for race and age by frequency. We have conducted a survey to determine the expected age range for cases. We anticipate a mean and median age of about 66 years for the prospective cases, which will permit an age matching with population-based controls using the established resources. Most patients will be in moderately good health, as they are identified at a relatively young age through PSA screening. Cases could be rendered more similar to controls with a selection criterion for controls that would achieve matching of cases based on census tract. This alternative would not eliminate a possible selection bias but would make the study substantially more difficult to perform. Also, our experience in Baltimore is that population control accrual is not skewed to one part of Baltimore. A 2002 survey for the ongoing lung cancer case-control study indicated that the recruited cases and population-based controls have a similar residential history. Thirty-eight percent of the cases were from Baltimore City versus 54% of the controls, and 62% of the cases lived in Baltimore suburbs or Eastern Shore counties versus 46% of the controls. We do not expect a selection bias based on genotype that would be confounded by behavior or education, as the genotype is unknown to the subjects and there is no plausible relation to either behavior or other factors that might affect the selection. A limitation common to other case-control studies is the possibility of differences between cases and the control population that are caused by a confounding disease, and not the disease under investigation (case identification among a hospitalized cohort, hospital-based controls). We are limiting the bias by matching cases with population-based, but not hospital-based, controls. The relatively young age of our cases will also limit this problem.

Another limitation relates to problems associated with rapid subject accrual. We expect to identify all cases through hospital pathology and oncology departments. This will be verified through tumor registry records at 6-months intervals. Based on our experience in the ongoing lung cancer case-control study, we expect to contact most of the subjects prior to treatment or surgery, but will confirm this during our pilot study. We will allow for accrual of subjects before and after surgery, which will give us more flexibility for the accrual process.

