1.2.2 RATIONALE FOR SELECTION OF SUBJECTS BY RACE

PCa has the largest health disparity for any cancer site in the US (52). The causes of this health disparity are multifactorial and may include tumor biology. African-American men have the highest incidence and mortality rates. The disease accounts for about 39% of all cancers diagnosed in African-American males (53). The age-adjusted African-American to Caucasian cancer incidence ratio is about 1.6 but the mortality rate is 2 to 3-fold higher for African-Americans than Caucasians (22). African-American men develop PCa at a younger age, and the disease progression is faster than in Caucasians (22). It is hypothesized that the tumor biology of PCa is different in the two ethnic groups.

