2.1.1 INCLUSION CRITERIA

CASES

- 1. Has been diagnosed with PCa within the last two years
- 2. Pathological diagnosis of PCa made
- 3. Must reside in Baltimore City or contiguous metropolitan counties, Anne Arundel and Prince George's counties, Eastern Shore, western and northern Maryland, or adjacent counties in Pennsylvania, Delaware, Virginia, or Washington DC area
- 4. Has a residential working phone within his home
- 5. Was born in the United States
- 6. Of African-American or Caucasian descent, and age 40 to 90 years
- 7. Speaks English well enough to be interviewed
- 8. Is physically and mentally capable of performing the interview
- 9. Never has been interviewed as a control for the study
- 10. A non-objection statement to contact the patient has been obtained from the treating physician at the hospital where the patient was identified, or from the physician who is listed as the treating physician

CONTROLS

- 1. Stratified to match cases by age (5-year intervals), gender and race
- 2. Must reside in Baltimore City or contiguous metropolitan counties, Anne Arundel and Prince George's counties, Eastern Shore, western and northern Maryland, or adjacent counties in Pennsylvania, Delaware, Virginia, or Washington DC area
- 3. Has a residential working phone within his house
- 4. Was born in the United States
- 5. Speaks English well enough to be interviewed
- 6. Is physically and mentally capable of performing the interview
- 7. Never has been interviewed as a control for the study (with our tracking database)

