Genome-wide gene expression analysis of prostate carcinomas will compare expression profiles among groups (e.g., African-American versus Caucasian, high versus low IGF-1) that consist of 10-30 tumors per group. The minimum number of tumors needed to generate a molecular profile that differentiates two groups cannot be determined for the proposed experiments. A best estimate is 13 per group based on the following assumptions: A significance level of 0.001 and a power of 0.05, assuming the data is base 2log transformed and that the variance in expression for a gene of interest is 0.5, and that one wishes to be able to detect genes for which one of the four subgroups exhibits a two-fold change in expression at the specified power (using the nQuery software). However, some recent PCa gene expression studies used fewer tissues than we are proposing for our experiments and yielded expression signatures that predicted clinical behavior in response to treatment (84,85) or differentiated tumors according to

NCI IRB Approval:	October 28, 2004
Protocol Number:	05-C-N021

the Gleason score (93). Thus, the proposed sample size for our investigations appears be adequate and is still suitable to do laser-captured microdissection. [name] at the Advanced Computing Center at the NCI-Frederick will conduct the analysis of the expression data.

Target Accrual Numbers of Cases and Controls ¹			
	African-American	Caucasian Males	Total
	Males		
Cases	500	500	1000
Population	500	500	1000
Controls			
Total	1000	1000	2000
¹ Race will be identified by subject self-report			

 Table 7: Target Accrual Numbers for the Proposed Study (as of 2010)

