wild-type genotype (major allele), or the lowest exposure subgroup, as the reference group. Odds ratios and 95% confidence intervals will be calculated by unconditional logistic regression. Regression analysis will be performed in univariate and multivariate models to assess associations between risk factors and cancer susceptibility, and to adjust for possible confounding factors. Case-case analyses, correlating tissue marker expression with tumor staging, hormone blood concentrations, diet or genotypes, will be done by ANOVA, with the student's t-test, or a nonparametric test, such as the Mann-Whitney U rank sum test. To look at trends, the Mantel-Haenszel test for trend will be used to assess the correlation between marker expression/frequency and categorized (e.g., low, medium, high) variables, such as tumor stage, intake of a dietary factor, or IGF-1 blood concentrations. The association between a genotype and outcome will be studied either in a logistic regression model after categorizing into a good and poor outcome group or with the Kaplan-Meier method and the log-rank test. All analyses will be performed with the STATA and SAS statistical software packages.

ANALYSIS OF GENE EXPRESSION PROFILES

The data from the Affymetrix HG-U133A array will be estimated using the RMA procedure from Bioconductor (www.bioconductor.org). Previous analysis on raw data from replicate samples with RMA indicates that the mean standard deviation of log2 intensities is 0.1 across all intensity levels. This corresponds to a typical technical error of 5%-10% (94).

The factorial study design suggests an analysis of variance. We will first examine the four groups for heterogeneity of variances by comparing the ratios of variances between groups to the F-distribution. If the distributions conform, we will follow standard ANOVA procedure. If there is significant departure from agreement, we will perform non-parametric ANOVA using the rank F-test and use the Welch t-test for two group comparisons. We will select differentially expressed genes for contrasts between racial groups at each level of tumor, and for the difference between tumor stages across racial groups. To address the multiple comparisons problem we will use a modified FDR procedure of Benjamini and Hochberg adapted to correlated data (95).

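### Race matching and a catchment described as narrow do not control ancestry within African-American men, so false-positive rates for ancestry-linked variants can rise by an amount the design cannot measure

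*Protocol*

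**What the plan says.** Protocol section 3.1.5 identifies the hazard itself: "If not addressed, the study may yield differences in genetic frequencies that are unrelated to the case status". Its stated remedy is that "we have restricted the study to a narrow geographic area, and will match for race and age by frequency". The section considers matching on census tract and declines it as too difficult. It then describes cases and controls in the lung study as having a similar residential history and gives the figures: "Thirty-eight percent of the cases were from Baltimore City versus 54% of the controls". That study recruits at the same two hospitals and shares its male controls with this one (protocol summary; section 1.2.1).

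Other passages bear on the same point:

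- **Catchment.** After Baltimore City, its contiguous counties, and Anne Arundel and Prince George's counties, section 2.1.1 adds "Eastern Shore, western and northern Maryland, or adjacent counties in Pennsylvania, Delaware, Virginia, or Washington DC area".
- **Race.** The footnote to Table 7 (section 5.4.1) states "Race will be identified by subject self-report", with two categories.
- **Birthplace.** Section 2.1.1 requires of cases and controls alike: "Was born in the United States".
- **Analysis.** Section 5.4.3 analyses all cases together and then by race, and uses multivariate regression "to adjust for possible confounding factors", without naming the factors.
- **Genotyping.** Section 3.1.4 lists DNA quality, assay controls and 10% blinded duplicates. It names no ancestry-informative or null markers.

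**The concern.** Matching, stratifying or adjusting on self-reported race balances the two groups as wholes. It does not balance the share of African ancestry, which can vary from man to man within the African-American group. If cases drawn from two hospitals and controls drawn from a motor-vehicle register differ in mean ancestry within that group, any variant whose frequency differs between the ancestral populations will differ between cases and controls without affecting risk.

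This matters because section 5.4.1 puts particular emphasis on genetic factors that might explain aggressive disease in African-American men. Variants whose frequency follows ancestry are natural candidates for that question and are the most exposed. Section 1.2.3 already cites one, SRD5A2 Val89Leu, whose frequency gradient across racial groups parallels risk. Under section 5.4.3, hypotheses supported by existing knowledge are tested at an unadjusted 0.05.

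The omission cannot be left to a later analysis plan. An analyst can adjust for ancestry only if it has been measured, and the choice of markers to genotype is made in this protocol.

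**Working it through.** **1. Text against text.** Section 3.1.5 calls the area narrow; section 2.1.1 admits men from much of Maryland, adjacent counties of three states and the Washington area. Section 3.1.5 calls residence similar; its own figures differ by 54 − 38 = 16 percentage points.

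**2. Unit of analysis.** Table 9 gives power 0.93 for an odds ratio of 1.5, prevalence 20%, 400 cases and 400 controls. Here p1 = 1.5 × 0.20 / (0.80 + 1.5 × 0.20) = 0.273. A two-proportion test on 800 against 800 alleles gives 0.929, which matches. Counting 400 against 400 men gives 0.678. The calculation below therefore also works with allele counts.

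**3. Effect of an ancestry gap on a null variant.**

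From the protocol: 500 cases and 500 controls per race (Table 7); two-sided alpha 0.05 (sections 5.4.2 and 5.4.3).

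Assumed, because the documents give no figure: overall allele frequency p = 0.40; a case-control gap *a* in mean African ancestry; a difference *D* in allele frequency between the ancestral populations.

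- Shift in mean allele count = 2 × a × D.
- Standard error = √(2 × 2 × 0.40 × 0.60 / 500) = 0.0438.
- z = shift / standard error.
- Rejection rate = Φ(z − 1.96) + Φ(−z − 1.96).

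Example: a = 0.05 and D = 0.5 give a shift of 0.050, z = 1.14 and a rejection rate of 20.7%.

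| Ancestry gap | D = 0.2 | D = 0.5 | D = 0.8 | Spurious odds ratio |
|---|---|---|---|---|
| 1 point | 5.1% | 5.6% | 6.5% | 1.01–1.03 |
| 2 points | 5.4% | 7.4% | 11.3% | 1.02–1.07 |
| 3 points | 5.9% | 10.5% | 19.5% | 1.03–1.10 |
| 5 points | 7.4% | 20.7% | 44.7% | 1.04–1.18 |

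The D = 0.8 column is extreme.

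**4. Sensitivity.** Replace p = 0.40 by mean African ancestry of 0.80 in controls and ancestral frequencies centred on 0.5. Over the same range of D, the rates become 5.1–6.9% (1 point), 5.4–13.1% (2 points) and 7.4–55.3% (5 points). The largest spurious odds ratio at 5 points is 1.25. On this basis a spurious odds ratio of 1.5 needs a gap of about 22, 14 or 9 points for D = 0.4, 0.6 or 0.8.

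**5. Sample size.** The same bias produces more false positives as enrolment grows. With p = 0.40, a 5-point gap and D = 0.8, the rate is 21.1% at 200/200 and 44.7% at 500/500.

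**6. What the residence gap alone could produce.** If city and non-city African-American men differed by an assumed 5 to 20 points in mean ancestry, the case-control gap would be 0.16 × 5 = 0.8 to 0.16 × 20 = 3.2 points.

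**The case against.** Several points on the other side are sound.

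- **Size is unknown and may be negligible.** The documents give neither a case-control ancestry gap nor ancestral allele frequencies. At 1 point, inflation is close to nil. The 38% versus 54% comparison concerns lung cancer cases, and section 5.4.2 says most of the 2001 prostate cases lived in greater Baltimore. This stands, and it limits the claim to a possibility.
- **Weak associations are disclaimed.** Section 5.4.2 says the study does not aim at odds ratios between 1 and 1.5 and calls them prone to confounding. The spurious values in the table fall in that band. But section 5.4.3 judges significance by alpha and sets no minimum odds ratio, so such a result could still be declared.
- **Other safeguards exist.** A reader might infer that matching and geography are the only control. They are not: US birth, analysis by race, multivariate adjustment, and the verification and later validation in section 1.2.3 also apply. None measures ancestry within race, and validation acts only after a variant has tested positive, though it does limit the consequences.
- **The unadjusted 0.05 is conditional.** It applies only where prior knowledge links the genotype to cancer risk; otherwise alpha is adjusted. The rates above are for the unadjusted case.
- **The incidence ratio is between races.** From "The age-adjusted African-American to Caucasian cancer incidence ratio is about 1.6" (section 1.2.2) a reader might infer that risk rises with ancestry among African-American men. The ratio does not show that.

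Section 3.1.5 also argues that men do not know their genotype and so cannot select on it. That answers self-selection by genotype, but not a difference in ancestry between the communities that supply cases and controls.

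**Conclusion.** The concern holds in a limited form. The protocol states that a recognised bias is corrected, its own eligibility list and residence figures undercut that statement, and nothing it plans measures ancestry within race. For ancestry-linked variants, the false-positive rate and the odds ratio in African-American men can be distorted to an extent the design can neither measure nor correct.

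On the assumptions in the table, the distortion runs from negligible at 1 point, through small at 2 points unless D is extreme, to serious at 5 points. Spurious odds ratios are mostly below 1.2.

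A reader might infer that ancestry-linked variants will test positive. The documents do not support that: in every row of the table most null variants would not reach significance, and no ancestry gap is documented. Nor do these figures suggest that confounding alone would usually produce an odds ratio of 1.5.

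**What to change.** 1. Add a set of ancestry-informative markers to the genotyping in section 3.1.4, run on the blood DNA of all cases and controls.
2. State in section 5.4.3 that estimated individual ancestry will be a covariate in the race-specific and pooled genotype models. To the extent the estimate is accurate, this returns a null variant to the nominal 5%.
3. In section 3.1.5, replace the statements that the area is narrow, that residences are similar and that the problem is corrected. Describe the actual catchment, the 16-point difference and the ancestry adjustment.

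The cost is a modest additional assay charge, for which the documents give no figure, and one covariate. No new subjects, visits or samples are needed, and section 3.1 places laboratory work after recruitment. Unlinked candidate variants genotyped for other purposes could serve as a rough check for inflation. They are not a substitute, because their number is not stated and they are chosen as disease candidates, not as neutral markers.
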